 - Sinus bradycardia (<50 beats/min), sinus nodal dysfunction (sick sinus disease), atrioventricular block of any degree (PR >200 msec), or any other bradycardia (<50 beats/min), except for patients with permanent pacemakers;
 - Cardiac infarction, cardiac surgery or cardiac insufficiency episode within the last 6 months;
 - Known abnormal value of left ventricular ejection fraction (LVEF <low limit of normal (LLN)), unless documented confirmation of recovery (LVEF >LLN) in the previous month;
 - QT interval corrected using Fridericia's formula (QTcF) >450 msec for males or >470 msec for females;
 - History of known congenital or acquired QT prolongation;
 - Uncorrected hypokalaemia, hypocalcaemia (adjusted) and/or hypomagnesemia at screening;
 - Troponin test performed at local laboratory >1.5 x ULN; or
 - Need for an unreplaceable drug that prolongs QT and it is clearly associated with a known risk for torsades de pointes (TdP) (category 1 of [Appendix 8a – Lists of Drugs That Prolong the QT Interval and/or Induce Torsades de Pointes Ventricular Arrhythmia](#)); in case of being already on treatment with these aforementioned drugs, a minimum of 4 half-lives of the drug is required before replacement (if feasible).
11. Hypersensitivity to the active ingredient or any of the excipients (mannitol, macrogolglycerol hydroxystearate, and ethanol) or patients for whom dexamethasone, antihistamine H1/H2 or antiserotonergic agents are contraindicated.
12. Females who are pregnant (negative serum or urine pregnancy test required for all females of child-bearing potential at screening) or breast feeding.
13. Females and males with partners of child-bearing potential (females who are not surgically sterile or postmenopausal defined as amenorrhea for >12 months) who are not using at least 1 protocol-specified method of contraception.
14. Any other clinically significant medical condition (including major surgery within the last 3 weeks before screening) or laboratory abnormality that, in the opinion of the investigator, would jeopardise the safety of the patient or potentially impact on patient compliance or the safety/efficacy observations in the study.

Test products, dose, and mode of administration:

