Plitidepsin for injection is provided in vials containing 2 mg plitidepsin powder. For administration, vial contents are reconstituted by addition of 4 mL of solvent for plitidepsin to obtain a slightly yellowish solution containing 0.5 mg/mL plitidepsin with mannitol, macrogolglycerol hydroxystearate, and ethanol excipients. The required amount of plitidepsin-reconstituted solution is added to a bag containing 0.9% sodium chloride or 5% glucose for IV injection and administered as an IV infusion over 60 minutes.

For prevention of plitidepsin-related infusion reactions, administration of the following premedications should be ideally completed 20 to 30 minutes before initiating the plitidepsin infusion and, exceptionally, up to 2 h before plitidepsin infusion start:

- Palonosetron 0.25 mg IV (tropisetron 5 mg IV could be considered if palonosetron is not available)
- Diphenhydramine hydrochloride 25 mg IV (or equivalent, such as dexchlorpheniramine maleate 5 mg)
- Ranitidine 50 mg IV (or equivalent, such as famotidine 20 mg IV)
- Dexamethasone phosphate 8 mg IV (equivalent to 6.6 mg of dexamethasone base)

Additionally, on Days 4 and 5 patients treated with plitidepsin must receive tropisetron 5 mg PO/IV if tropisetron 5 mg IV was administered on Days 1, 2, and 3.

Reference therapy, dose, dose form, and mode of administration:

Dexamethasone: Patients on both plitidepsin and control arms will receive dexamethasone phosphate 8 mg/day (equivalent to 6.6 mg of dexamethasone base) IV on Days 1 to 3 (administered as a premedication in plitidepsin arms), followed by dexamethasone phosphate 7.2 mg/day (equivalent to 6 mg of dexamethasone base) PO/IV from Day 4 and up to a total cumulative dose of 60 mg of dexamethasone base (as per physician judgement according to patient clinical condition and evolution).

Remdesivir: Consistent with local treatment guidelines, patients randomised to the control arm may receive remdesivir 200 mg IV on Day 1 followed by 100 mg/day IV on Days 2 to 5.

Favipiravir: Consistent with local treatment guidelines, patients randomised to the control arm may receive favipiravir 1600 mg BID PO on Day 1, followed by 600 mg BID PO daily for 2 to 5 days.

Best Supportive Care (BSC): BSC consistent with National Institute of Health COVID-19 treatment guidelines (www.covid19treatmentguidelines.nih.gov) or local country guidelines will be provided to all study participants.

Duration of patient participation in study:

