Additional information about preclinical studies performed to evaluate pharmacokinetics (PK), safety pharmacology, and toxicology of plitidepsin may be found in the IB.

Safety in COVID-19 Patients

Study APLICOV-PC was a Phase 1, multicentre, open-label study in which 45 patients hospitalised for management of COVID-19 were randomised into 3 dose groups, comprising 1.5, 2.0, and 2.5 mg plitidepsin administered as a 1.5-hour IV infusion once a day for 3 consecutive days.³⁰ The primary objective of this study was to determine the safety and toxicological profile at each dose level, based on (1) frequency of Grade ≥ 3 treatment-emergent adverse events (TEAEs) at Days 3, 7, 15, and 31 according to National Cancer Institute (NCI)-Common Terminology Criteria for Adverse Events (CTCAE) version 5.0; (2) percentage of patients unable to complete treatment and reasons; (3) percentage of patients with TEAEs and serious adverse event (SAEs) at Days 3, 7, 15, and 31; and (4) change from baseline haematologic and non-haematologic parameters on Days 3, 7, 15, and 31. A secondary objective was to select a recommended dose for a pivotal study.

Findings for protocol-specified safety endpoints are summarised as follows:

- Grade ≥ 3 AEs: 31% (14/45) of patients experienced Grade ≥ 3 AEs ([Table 1](#)) and only 2 patients experienced a treatment-related Grade ≥ 3 AE: one case of anaphylactic reaction during the first plitidepsin infusion that resulted in treatment discontinuation and one case of diarrhoea that had no impact on plitidepsin treatment. Consistent with Grade ≥ 3 AEs being predominantly due to COVID-19 infection, the prevalence of Grade ≥ 3 AEs largely reflected the percentage of patients with mild disease in each cohort, with the highest prevalence in the 2.5-mg cohort (6.7% with mild disease, 40.0% Grade ≥ 3 AEs), a lower percentage in the 1.5-mg cohort (13.3% with mild disease, 33.3% Grade ≥ 3 AEs), and the lowest percentage in the 2.0-mg cohort (20.0% with mild disease, 20.0% Grade ≥ 3 AEs). No events of special interest occurred, with the exception of one case of Grade ≥ 3 ALT elevation.
- Patients unable to complete treatment: Only one patient was unable to complete plitidepsin treatment, after experiencing an anaphylactic reaction within the first 5 minutes after starting infusion.

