- Troponin test performed at local laboratory >1.5 x ULN; or
- Need for an unreplaceable drug that prolongs QT and it is clearly associated with a known risk for torsades de pointes (TdP) ([Appendix 8a - Lists of Drugs That Prolong the QT Interval and/or Induce Torsades de Pointes Ventricular Arrhythmia](#)); in case of being already on treatment with these aforementioned drugs, a minimum of 4 half-lives of the drug is required before replacement (if feasible).

11. Hypersensitivity to the active ingredient or any of the excipients (mannitol, macrogolglycerol hydroxystearate, and ethanol) or patients for whom dexamethasone, antihistamine H1/H2 or antiserotonergic agents are contraindicated.

12. Females who are pregnant (negative serum or urine pregnancy test required for all females of child-bearing potential at screening) or breast feeding.
13. Females and males with partners of child-bearing potential (females who are not surgically sterile or postmenopausal defined as amenorrhoea for >12 months) who are not using at least 1 protocol-specified method of contraception.
14. Any other clinically significant medical condition (including major surgery within the last 3 weeks before screening) or laboratory abnormality that, in the opinion of the investigator, would jeopardise the safety of the patient or potentially impact on patient compliance or the safety/efficacy observations in the study.

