5.1. Treatments Administered

INN name	Plitidepsin
Pharmaceutical form	Powder and solvent for concentrate for solution of infusion
Formulation	
Plitidepsin 2 mg powder is provided as a sterile, preservative-free, and white to off-white lyophilised powder/cake comprising 2 mg plitidepsin and [REDACTED] mannitol in a single-dose, 10 mL clear type 1 glass vial.
 
Solvent for plitidepsin is provided as a sterile, preservative-free, clear, slightly viscous aqueous liquid (4 mL) containing [REDACTED] macrogolglycerol ricinoleate and [REDACTED] ethanol in a single-dose type 1 clear glass ampoule.
 
For administration, vial contents are reconstituted by addition of 4 mL of solvent for plitidepsin to obtain a slightly yellowish solution containing 0.5 mg/mL plitidepsin with mannitol, macrogolglycerol ricinoleate and ethanol excipients. The required amount of plitidepsin reconstituted solution is added to bag containing 0.9% sodium chloride or 5% glucose for IV injection and administered as an IV infusion over 60 minutes.

Packaging and labelling	Packaging and labelling will be in accordance with applicable local regulatory requirements and applicable Good Manufacturing Practice (GMP) guidelines.
Storage	
Plitidepsin should be stored refrigerated between 2°C and 8°C and the vials should be kept in the outer carton to protect them from light. Excursions in temperature between 0°C and 15°C that may be experienced during shipping and distribution may be allowed. Do not freeze.
 
The drug in these conditions is stable for 60 months.
 
The plitidepsin solution for infusion should be administered within 6 hours of reconstitution (time of administration to the patient included) if stored at room temperature and under ambient lighting. If storage is required prior to administration, then solutions should be stored refrigerated and protected from light and should be used within 24 hours of reconstitution.
 
Plitidepsin is a cytotoxic medicinal product. Any unused medicinal product or waste material should be disposed of in accordance with local requirements.

Manufacturer	Pharma Mar S.A., Madrid, Spain
INN Name	Dexamethasone Remdesivir Favipiravir
Detailed information about the formulation, posology, packaging and labelling, storage, and manufacturer is provided in the current country-specific product information. The SmPC and/or leaflet provides detailed product information for investigators in the European Union and/or in other regions.	

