Plitidepsin will be supplied by the sponsor along with the (batch/lot) numbers and certificates of analysis. Commercially available formulations of dexamethasone and remdesivir, favipiravir, or other regulatory-approved antiviral treatment will be provided, as appropriate. A certificate of release authorised by a qualified person in the European Union will also be issued for the investigational medicinal product (IMP). One vial of plitidepsin for injection, 2 mg, and 1 ampoule of solvent for plitidepsin, 4 mL, are packaged in a carton, which is required for light protection. Plitidepsin for injection is provided in vials containing 2 mg plitidepsin powder. For administration, vial contents are reconstituted by addition of 4 mL of solvent for plitidepsin to obtain a slightly yellowish solution containing 0.5 mg/mL plitidepsin with mannitol, macrogolglycerol ricinoleate and ethanol excipients. The required amount of plitidepsin-reconstituted solution is added to bag containing 0.9% sodium chloride or 5% glucose for IV injection and administered as an IV infusion over 60 minutes.

Plitidepsin vials should be stored refrigerated between 2°C and 8°C. Excursions in temperature between 0°C and 15°C that may be experienced during shipping and distribution may be allowed. Do not freeze.

The pharmacist at each investigational site will be responsible for management of the IMP (plitidepsin, dexamethasone, and any regulatory approved antiviral treatment, such as remdesivir or favipiravir). The pharmacist will inventory and acknowledge receipt of all shipments of IMP, which must be kept in a locked area with restricted access. The IMP must be stored and handled in accordance with the manufacturer's instructions and temperature traceability is required. The pharmacist will keep accurate reconstitution and dilution records of the quantities (and batch numbers) of IMP dispensed and used for each patient. Periodically, the sponsor's study monitor will check the reconstitution, dilution, supplies of IMP held by the pharmacist to verify accountability of all IMP. All delivery records must be reconciled with usage records. It is essential that all IMP be accounted for by the site's pharmacist and that discrepancies are explained and documented.

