7.2.1. Adverse Events

Adverse event definitions and assignment of severity and causality are detailed in [Appendix 1](#). All adverse events (AE) and adverse reactions (ARs), based on clinical signs and symptoms and laboratory measurements, will be measured daily until Day 31 (± 3 days), except treatment-related adverse events, treatment-emergent adverse events of special interest, and SAEs that will be measured daily until resolution or stabilisation to at least Grade 1, or to an acceptable level according to the investigator and the sponsor of his/her designated representative.

Adverse events will be elicited from the patient (or, when appropriate, from a caregiver, surrogate, or the patient's legally authorised representative) by the study site staff using a non-leading question such as "How are you feeling today?" or "Have you had any health concerns since your last visit?"

The investigator and any designees are responsible for detecting, documenting, and reporting events that meet the definition of an AE or SAE and remain responsible for following up AEs that are serious, considered related to the study treatment or the study, or that caused the patient to discontinue the study treatment (see [Section 4.4.2](#)).

Clinical Signs and Symptoms: AEs, including worsening of baseline signs and symptoms of disease observed by the investigator (preferably by the same physician for a same patient) or reported by patients to study nurses will be recorded and graded according to NCI-CTCAE version 5.0, accessible via internet

(http://ctep.cancer.gov/protocolDevelopment/electronic_applications/docs/CTCAE_v5_Quick_Reference_8.5x11.pdf). All events, including those considered not related to the study drugs, must be reported in the eCRF.

The following AEs will be considered and monitored as AEs of special interest: musculoskeletal disorders, CPK increases, and rhabdomyolysis; hypersensitivity reactions, cardiac events and transaminase elevations, and hepatobiliary disorders.

Laboratory Abnormalities: Laboratory abnormalities will be recorded and graded according to NCI-CTCAE version 5.0, accessible via internet (http://ctep.cancer.gov/protocolDevelopment/electronic_applications/docs/CTCAE_v5_Quick_Reference_8.5x11.pdf). Laboratory abnormalities that are of clinical significance will be recorded in Adverse Event eCRF.

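### The protocol names two different excipients for the same plitidepsin solvent: macrogolglycerol hydroxystearate in exclusion 11 and the synopsis, macrogolglycerol ricinoleate in Section 5.1

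*Protocol*

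**What the plan says.** Three places name macrogolglycerol hydroxystearate:

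- Section 4.2, exclusion criterion 11: "Hypersensitivity to the active ingredient or any of the excipients (mannitol, macrogolglycerol hydroxystearate, and ethanol").
- Synopsis, exclusion criterion 11, in the same terms: "any of the excipients (mannitol, macrogolglycerol hydroxystearate, and ethanol").
- Synopsis, test products, on the reconstituted solution: "plitidepsin with mannitol, macrogolglycerol hydroxystearate, and ethanol excipients".

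Three places, all in Section 5.1, name macrogolglycerol ricinoleate:

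- The formulation entry for the solvent ampoule: "slightly viscous aqueous liquid (4 mL) containing [REDACTED] macrogolglycerol ricinoleate and [REDACTED] ethanol in a single-dose type 1 clear glass ampoule".
- The same entry, on the reconstituted solution: "with mannitol, macrogolglycerol ricinoleate and ethanol excipients".
- The text on preparation, storage and handling: "plitidepsin with mannitol, macrogolglycerol ricinoleate and ethanol excipients".

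Two other statements bear on why the name matters. Section 7.2.1 includes among the adverse events of special interest "hypersensitivity reactions, cardiac events and transaminase elevations, and hepatobiliary disorders". Section 1.2, reporting the earlier study of plitidepsin in 45 COVID-19 patients, describes "one case of anaphylactic reaction during the first plitidepsin infusion that resulted in treatment discontinuation".

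**The concern.** Exclusion 11 is the only eligibility criterion that spells out which excipients to check against a patient's allergy history. If Section 5.1 gives the true composition, that list leaves out a substance the patient will receive intravenously and names one that the product does not contain. A site working from the list would then ask about the wrong substance. If the synopsis gives the true composition, the eligibility text stands, but the formulation and preparation text that pharmacists work from is wrong.

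The matter concerns safety screening and the consistency of operative text. It has no bearing on the endpoint, the type I error, the power or any analysis.

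**Working it through.** The protocol states no figure to reproduce, so the check is a comparison of text, with a little arithmetic to show how widely the solvent is used.

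**Do the descriptions concern one product?** The synopsis product description and both reconstitution descriptions in Section 5.1 give the same steps: a 2 mg vial, 4 mL of the plitidepsin solvent, a 0.5 mg/mL solution, further dilution in saline or glucose, and a 60-minute infusion. The synopsis text and the Section 5.1 preparation text run nearly in parallel, and the excipient name is the substantive difference. The protocol describes no second solvent or formulation.

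**Could it be an artefact?** The blacked-out items in the ampoule entry stand before the excipient names, and the names themselves are legible. None of the six mentions is in an amendment log. A misreading of the PDF would not swap two dissimilar words consistently by section.

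**Could both names be right?** The protocol nowhere says that the two names are equivalent.

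**Count of mentions**

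| Name | Where | Count |
|---|---|---|
| Hydroxystearate | Synopsis exclusion 11; synopsis test products; Section 4.2 exclusion 11 | 1 + 1 + 1 = 3 |
| Ricinoleate | Section 5.1 formulation (twice); Section 5.1 preparation | 2 + 1 = 3 |

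The count cannot settle which is correct, since neither name is an isolated slip.

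**Planned exposure to the solvent** (context only)

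- Patients in the two plitidepsin arms: 2 × 203 = 406, if neither arm is dropped at the futility analysis.
- Reconstituted solution per dose: 1.5 mg ÷ 0.5 mg/mL = 3 mL, or 2.5 mg ÷ 0.5 mg/mL = 5 mL.
- Over Days 1 to 3: 3 × 3 = 9 mL, or 3 × 5 = 15 mL. These are volumes of the reconstituted solution, not amounts of the excipient.

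**Earlier anaphylactic reaction** (context only)

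- 1/45 = 2.2%, Clopper-Pearson 95% confidence interval 0.06% to 11.8%. The protocol classes the reaction as treatment-related but does not attribute it to any component, so this is not an estimate of the risk from either excipient.

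**The case against.** The strongest reply is that the exclusion rule works despite the wrong name. It covers hypersensitivity to any of the excipients, and the parenthesis only lists them, so a patient known to react to the component actually present is excluded under either name. Exclusion 14 also lets the investigator exclude anyone whose condition would put safety at risk. For harm to follow, a patient must have a documented allergy to this particular excipient, and the site must read the parenthesis but not Section 5.1. The protocol gives no frequency for either.

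Other safeguards exist too. Premedication with H1 and H2 antihistamines and dexamethasone precedes each infusion (Section 5.1), and Section 6.2 sets out graded management of infusion reactions, with permanent discontinuation for Grade 3 to 4. The protocol also refers investigators to the Investigator's Brochure, which is not at hand and may give the composition correctly.

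Much of this stands, and it keeps the point modest. It does not remove it. The general wording protects only if the site knows what the product contains, and that is where the protocol contradicts itself. Premedication and reaction management reduce the consequences of a reaction but do not replace screening. Exclusion 11 does not send the reader to the Brochure.

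It is also fair to say that the exposure volumes and the anaphylaxis rate do not measure the effect of a naming error. They show only that the solvent is widely used and that hypersensitivity is a recognised risk in this programme.

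**Conclusion.** The contradiction is real: three mentions of each name, for one product, in current operative text. At least one of the exclusion list and the Section 5.1 formulation and preparation text is wrong as written, and the protocol does not show which. This rests on one assumption, that the two names denote different substances, which is how the protocol's own text reads.

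The weight is moderate. The point should be corrected because it sits in a hypersensitivity exclusion and in the preparation text for an infused drug planned for up to 406 patients. It is an internal inconsistency with partial safeguards. No number of patients harmed is claimed.

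**What to change.** Verify the solvent composition against the product specification, then use that one name in exclusion 11 (synopsis and Section 4.2), in the synopsis product description and in all three places in Section 5.1.

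Until the check is complete, list both names in exclusion 11. This may print an excipient that the product does not contain, but it closes the screening gap whichever name is right. It does not resolve the Section 5.1 text, so it is a stopgap only.

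The cost is one check and a clarification letter or amendment wording. Sample size and analysis do not change.

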4.3. Disease Diagnostic Criteria

Patients with a documented diagnosis of SARS-CoV-2 infection performed by a local laboratory through either qualitative PCR, antigen test, or any other validated method approved by the local health authority, from appropriate biological samples collected no more than 72 hours before study treatment on Day 1, meeting category 5 on the 11-point WHO Clinical Progression Scale ([Appendix 13 - World Health Organization \(WHO\) Clinical Progression Scale](#)), and symptoms onset not beyond 14 days before initiation of study treatment, are required for enrolment. In the case that the patient had experienced more than one COVID-19 episodes, onset of symptoms should be referred to the most recent one.

4.4. Discontinuation Criteria

4.4.1. Screen Failures

Screen failures are defined as patients who consent to participate in the clinical study but are not subsequently enrolled in the study. A minimal set of screen failure information is required to ensure transparent reporting of screen failure patients to meet the Consolidated Standards of Reporting Trials (CONSORT) publishing requirements and to respond to queries from regulatory authorities. Minimal information includes demography, screen failure details, eligibility criteria, and any SAEs related to the study participation. Rescreening is not allowed in this study.

